- It is **not** acceptable for the PI to send photocopies of the subject's medical records to the Allergan Medical Safety Physician in lieu of completion of the AE/ADE/SAE/SADE eCRF page.
- There may be instances when copies of medical records for certain cases are requested by the Allergan Medical Safety Physician. In this case, all subject identifiers, with the exception of the subject number, will be redacted on the copies of the medical records before submission to the Allergan Medical Safety Physician.
- The PI will attempt to establish a diagnosis of the event based on signs, symptoms, and/or other clinical information. Whenever possible, the diagnosis (not the individual signs/symptoms) will be documented as the event.

Procedures for Reporting an AE or ADE

All AEs/ADEs occurring during the study period (beginning with signing ICF) are to be recorded on the appropriate CRF. For any treatment-related AE/ADE that is ongoing at the exit, the PI/TI will attempt to follow the subject until the AE/ADE has been resolved or follow-up is no longer possible.

AEs/ADEs that start after the study follow-up period has ended will be considered outside the scope of the study but will be captured.

Procedures for Reporting an SAE or SADE

All SAEs and SADEs occurring during the study period (beginning with signing ICF) are to be immediately reported to a sponsor representative at a fax number/email address listed on the cover page and recorded on the appropriate CRFs. All subjects with an SAE/SADE must be followed up and the outcomes reported. The PI is to supply the sponsor and the IRB with any additional requested information (eg, hospital discharge summary, autopsy reports, and terminal medical reports). The sponsor will evaluate all SADEs and determine and document in writing whether they meet the definition of UADE. These shall be reported to all participating PIs, the regulatory authorities, and IRBs as required by national regulations.

In the event of an SAE/SADE, the PI must:

- Notify the sponsor immediately by fax/email using the SAE/SADE reporting forms. For the SAE/SADE fax number/email address, see the [front page](#) of the protocol.
- Obtain and maintain in his/her files all pertinent medical records, information, and medical judgments from colleagues who assisted in the treatment and follow-up of the subject.
- Provide the sponsor with a complete, written case history which includes a statement as to whether the event was or was not related to the use of the investigational device.
- Promptly inform the governing IRB of the event, if it is treatment-related. For other SAEs, notify the governing IRB as required by the IRB, local regulations, and the governing health authorities.

12.4 Appendix 4: Medical Device Incidents: Definition and Procedures for Recording, Evaluating, Follow-up, and Reporting

Definitions of a Medical Device Incident

The detection and documentation procedures described in this protocol apply to all sponsor medical devices provided for use in the study (see [Section 7.1](#) for the list of sponsor medical devices).

Medical Device Incident Definition

A medical device incident is any malfunction or deterioration in the characteristics and/or performance of a device as well as any inadequacy in the labeling or the instructions for use which, directly or indirectly, might lead to or might have led to the death of a subject/user/other person or to a serious deterioration in his/her state of health.

Not all incidents lead to death or serious deterioration in health. The nonoccurrence of such a result might have been due to other fortunate circumstances or to the intervention of health care personnel.

It is sufficient that:

- An **incident** associated with a device happened

AND

- The **incident** was such that, if it occurred again, might lead to death or a serious deterioration in health.

A serious deterioration in state of health can include any of the following:

- Life-threatening illness
- Permanent impairment of body function or permanent damage to body structure
- Condition necessitating medical or surgical intervention to prevent one of the above
- Fetal distress, fetal death, or any congenital abnormality or birth defects

Examples of Incidents

- A subject, user, caregiver, or healthcare professional is injured as a result of a medical device failure or its misuse.
- A subject's study treatment is interrupted or compromised by a medical device failure.
- A misdiagnosis due to medical device failure leads to inappropriate treatment.
- A subject's health deteriorates due to medical device failure.

Documenting Medical Device Incidents**Medical Device Incident Documenting**

- Any medical device incident occurring during the study will be documented in the subject's medical records, in accordance with the investigator's normal clinical practice, and on the appropriate form of the CRF.
- For incidents fulfilling the definition of an AE or an SAE, the appropriate AE/SAE CRF page will be completed as described in [Appendix 12.3](#).
- The CRF will be completed as thoroughly as possible and signed by the investigator before transmittal to the sponsor or designee.
- It is very important that the investigator provides his/her assessment of causality (relationship to the medical device provided by the sponsor) at the time of the initial AE or SAE report and describes any corrective or remedial actions taken to prevent recurrence of the incident.
- A remedial action is any action other than routine maintenance or servicing of a medical device where such action is necessary to prevent recurrence of an incident. This includes any amendment to the device design to prevent recurrence.

Device Deficiency

A device deficiency is defined in accordance with ISO 14155 as “inadequacy of a medical device with respect to its identity, quality, durability, reliability, safety, or performance.” Device deficiencies include malfunctions, use errors, and inadequate labeling.

If a device deficiency occurs, the PI/TI or designee will notify the sponsor using the fax number or email on the front page of the protocol. Device deficiencies shall be documented throughout the study and appropriately managed by the sponsor. The sponsor shall review all device deficiencies and determine and document in writing whether they could have led to an SADE. These shall be reported to the regulatory authorities and IRBs as required by national regulations.

12.5

Appendix 5: Standard Discontinuation Criteria

CDISC Submission Value	CDISC Definition
Adverse event	Any untoward medical occurrence in a patient or clinical investigation subject administered a pharmaceutical product and which does not necessarily have a causal relationship with this treatment. An adverse event (AE) can therefore be an / unintended sign (including an abnormal laboratory finding), symptom, or disease temporally associated with the use of a medicinal (investigational) product, whether or not related to the medicinal (investigational) product. For further information, see the ICH Guideline for Clinical Safety Data Management: Definitions and Standards for Expedited Reporting. [Modified from ICH E2A] Synonyms: side effect, adverse experience. See also serious adverse event, serious adverse experience. (CDISC glossary)
Death	The absence of life or state of being dead (NCI)
Lost to follow-up	The loss or lack of continuation of a subject to follow-up
Physician decision	A position, opinion or judgment reached after consideration by a physician with reference to subject (NCI)
Pregnancy	Pregnancy is the state or condition of having a developing embryo or fetus in the body (uterus), after union of an ovum and spermatozoon, during the period from conception to birth. (NCI)
Protocol deviation	An event or decision that stands in contrast to the guidelines set out by the protocol (NCI)
Screen failure	The potential subject who does not meet one or more criteria required for participation in a study
Site terminated by sponsor	An indication that a clinical study was stopped at a particular site by its sponsor (NCI)
Study terminated by sponsor	An indication that a clinical study was stopped by its sponsor (NCI)
Withdrawal by subject	An indication that a study subject has removed itself from the study (NCI)

12.6 Appendix 6: Study Tabular Summary

Parameter Group	Parameter	Value
Study information	Study Title	A Randomized, Multicenter, Evaluator-blind, Controlled Study to Evaluate the Safety and Effectiveness of JUVÉDERM VOLITE™ XC Injectable Gel for the Improvement in Cheek Skin Smoothness
	Clinical Study Sponsor	Allergan
	Study Phase Classification	IDE
	Study Indication	Cheek skin smoothness
	Study Indication Type	Treatment
	Study Type	Effectiveness Safety
	Study Length	20 months
	Planned Country of Investigational Sites	US
	Planned Number of Subjects	263
	FD A-Regulated Device Study Indicator	Yes
	FD A-Regulated Drug Study Indicator	No
	Pediatric Study Indicator	No
Subject information	Diagnosis Group	Cheek skin smoothness
	Healthy Subject Indicator	N/A
	Planned Minimum Age of Subjects	22
	Planned Maximum Age of Subjects	None
	Sex of Subjects	Both
	Stable Disease Minimum Duration	N/A

Treatments	Investigational Therapy or Treatment	JUVÉDERM VOLITE™ XC Injectable Gel
	Intervention Type	Device
	Pharmacological Class of Invest. Therapy	N/A
	Dose per Administration	Up to 4 mL (initial and repeat); up to 2 mL (touch-up)
	Dose Units	mL
	Treatment Frequency	Initial, touch-up, and repeat (treatment group only) treatments
	Route of Administration	Injection
	Current Therapy or Treatment	N/A
	Added on to Existing Treatments	No
	Control Type	No-treatment control
	Comparative Treatment Name	None
Trial design	Study Type	Interventional
	Intervention Model	Parallel
	Planned Number of Arms	2
	Study is Randomized	Yes
	Randomization Quotient	2:1
	Study Blinding/Masking Schema	Single blind
	Stratification Factor	None
	Adaptive Design	No
	Study Stop Rules	Yes

12.7 Appendix 7: Protocol Amendment History

The protocol amendment [summary of change table](#) for the current amendment is located directly before the table of contents.

Amendment 2 (3 July 2019)

Overall Rationale for the Amendment:

Allow for enrollment of a Fitzpatrick skin phototype V/VI safety cohort.

Section No. and Name	Description of Change	Brief Rationale
Synopsis and 6.1 Inclusion Criteria	Revised inclusion criteria 2 and 3 to allow less stringent criteria for the Fitzpatrick V/VI safety cohort	To ensure adequate enrollment of subjects with Fitzpatrick skin phototypes V and VI
5.1 Overall Design	Added a sentence stating that up to 10 subjects may be enrolled in the Fitzpatrick V/VI safety cohort and followed for safety only	To ensure adequate enrollment of subjects with Fitzpatrick skin phototypes V and VI
6. Study Population	Specified that up to 10 subjects may be enrolled in the Fitzpatrick V/VI safety cohort and followed for safety only	To ensure adequate enrollment of subjects with Fitzpatrick skin phototypes V and VI
6.4 Screen Failures	Specified that screen failures may be rescreened if they are eligible for the Fitzpatrick V/VI safety cohort	To ensure adequate enrollment of subjects with Fitzpatrick skin phototypes V and VI
10.2 Populations for Analyses	Specified that the Fitzpatrick V/VI safety cohort will be included in the safety population for safety analyses and excluded from the ITT population for effectiveness analyses	To specify statistical reporting for the new Fitzpatrick V/VI safety cohort

Amendment 1 (28 February 2019)

Overall Rationale for the Amendment:

Clarifications to assist sites with study execution.

Section No. and Name	Description of Change	Brief Rationale
Title Page	Added IDE number	To include Regulatory Agency identifying number
Section 1 and Table 2-1 Screening Visit Procedures	Clarified that ACSS and FACE-Q are only to be performed on day of randomization if randomization occurs on a different day than screening	To clarify procedures
Table 2-1 Treatment Group Procedures	Clarified the order of procedures	To clarify the order and timing of procedures
Table 2-3 Control Group	Clarified the order of procedures	To clarify the order and

Procedures		timing of procedures
Table 2-4 Control Group Procedures	Clarified the order of procedures and removed skin hydration assessment at initial treatment for control group since it is already assessed at Month 1 in no-treatment period	To clarify the order and timing of procedures and remove redundant assessment
9. Study Assessments and Procedures	Clarified that ACSS and FACE-Q are only to be performed on day of randomization if randomization occurs on a different day than screening	To clarify procedures
9.3.1 Primary Effectiveness Measure	Added detail about ACSS features	To better describe the primary effectiveness measure
9.5.1 Time Period and Frequency for Collecting AE/ADE and SAE/SADE Information	Revised 1 sentence to align with current protocol template	To align with current protocol template
12.3 Appendix 3: Adverse Events	Deleted 1 sentence to align with current protocol template	To align with current protocol template

1.1. Objectives and Endpoints

Please refer to [Section 4.1](#) of study protocol.

1.2. Study Design

[figure not shown]
Study 1867-701-008 is a multicenter, evaluator-blind, controlled, parallel-design, prospective study of adults seeking improvement in cheek skin smoothness. The cheek skin smoothness will be assessed based on ACSS scores, ranging from 0 to 4 (none to extreme). Participants randomized to JUVÉDERM VOLITE XC will receive injectable gel in multiple microdepot injections across both cheeks. The following treatment groups are defined for this study:

- VOLITE: JUVÉDERM VOLITE™ XC injectable gel
- Control: No-treatment

Up to 263 participants will be enrolled, and approximately 210 participants from maximum 20 investigational sites will be randomized at a 2:1 ratio to treatment group and control group. Each site will have a blinded evaluating investigator (EI) and a principal investigator (PI) who is responsible for the overall conduct of the study at that site and may also be the treating investigator (TI). The TI performs all study treatments, and the blinded EI evaluates ACSS, AFLS, and skin hydration measurements.

The study design is presented in [Figure 1-1](#). Treatment group participants receive initial treatment and optional touch-up treatment at 30 days if needed to achieve optimal correction. Follow-up visits are 3 days after each treatment (collection of only safety data) and at Months 1, 2, 4, and 6 after the preceding treatment. Participants exit the study at Month 6 or receive repeat treatment and are followed at Day 3 and Months 1 and 4 after repeat treatment. Control group participants are followed for 1 month after randomization (the ‘no-treatment control’ period) and then either exit the study or receive optional treatment (initial and touch-up, if needed) in the delayed treatment period. Post-treatment follow-up visits are 3 days after each treatment and at Months 1, 2, 4, and 6 after the preceding treatment.

To ensure adequate enrollment of participants with Fitzpatrick skin phototype V and VI, up to 10 participants may be enrolled in the Fitzpatrick V/VI safety cohort with less stringent inclusion criteria (see protocol [Section 6.1](#)) and followed for safety only.

Figure 1-1 Study Design

2. Statistical Hypotheses

The primary effectiveness variable is the cheek skin smoothness based on the ACSS evaluated by EIs. The primary effectiveness endpoint is the ACSS responders at Month 1 defined as a participant who achieves at least a 1-point improvement from baseline on both cheeks based on ACSS. Month 1 refers to 1 month after the preceding treatment (initial or touch-up) for participants in the JUVÉDERM VOLITE XC treatment group or 1 month after randomization for participants in the no-treatment control group.

The null hypothesis is that there is no difference between the JUVÉDERM VOLITE XC treatment group and the no-treatment control group in the ACSS responder rate at Month 1. The alternative hypothesis is that there is difference between the JUVÉDERM VOLITE XC treatment group and the no-treatment control group in the ACSS responder rate at Month 1. These hypotheses are stated as:

$$H_0: P_v - P_c = 0$$

$$H_a: P_v - P_c > 0 \text{ or } P_v - P_c < 0$$

where P_v and P_c denote the responder rates for the JUVÉDERM VOLITE XC group at Month 1 after the preceding treatment (initial or touch-up) and for the no-treatment control group at Month 1 after randomization, respectively. The treatment effects between JUVÉDERM VOLITE XC and the no-treatment control group will be compared using the statistical method described in [Section 5.3.2](#). If the 2-sided p-value is less than 0.05 and the responder rate is greater for JUVÉDERM VOLITE XC than for the no-treatment control group, then JUVÉDERM VOLITE XC will be considered superior to the no-treatment control group.

3. Sample Size Determination

A sample size of 112 participants in the treatment group and 56 participants in the control group will provide 99.9% power to detect a difference of at least 40% in the responder rates on the ACSS between the groups, based on a 2-sided Fisher's exact test at the 5% level. The treatment group is assumed to have at least an 80% responder rate at Month 1, and the control group is assumed to have at most a 40% responder rate. The assumptions of responder rates are estimated from Allergan Study V12-001. Accounting for participant attrition of 20% during the study, 210 participants will be randomized at a 2:1 ratio to treatment group and control group. Randomization will occur within each study site.

Among the 210 participants randomized, at least 135 participants are expected to have a baseline AFLS score of 2 on both cheeks or 3 on both cheeks. The number of participants with baseline AFLS score of 0, 1, or 4 on either cheek, or 2 on one cheek and 3 on the other cheek is not expected to exceed 75. Assuming at least 65% of participants will have baseline AFLS score of 2 on both cheeks or 3 on both cheeks, 72 participants in treatment group and 36 participants in control group will provide 94.4% power to detect a difference of at least 35% in the responder rates on AFLS between the treatment groups, based on a 2-sided Fisher's exact test at the 5% level. The treatment group is assumed to have at least an 80% responder rate at Month 1, and the control group is assumed to have at most a 45% responder rate. The assumptions of responder rates are estimated from Allergan Study V12-001.

The sample size calculations used an inequality test for 2 proportions to demonstrate that the treatment group is superior to the control group.

Assuming 119 participants from the treatment group and 28 participants from the control group will be treated, a total of 147 treated participants will provide 95% power to detect an AE related to treatment with an incidence rate of 2% in the population using a 1-sided exact binomial test at the 2.5% level.

The commercial software, PASS (2008, Version 8.0.13), was used for the power calculations.

4. Populations for Analysis

The analysis populations will consist of participants as defined in Table 4-1.

Table 4-1 Analysis Populations

Population	Definition	Study Treatment Assignment
mITT	All randomized participants who have baseline assessment on the ACSS scale for both cheeks, and are not in the Fitzpatrick V/VI safety cohort (see the definition below)	As randomized
Observed Primary Endpoint	All mITT participants who have Month 1 assessment on the ACSS scale for both cheeks	As randomized
Safety	All participants who are randomized and received study intervention (VOLITE or no treatment)	As treated
VOLITE Treated (VT)	Participants randomized and received VOLITE treatment at the beginning of the Control Period, or Participants randomized and received optional VOLITE treatment after the Control Period.	As treated
VOLITE Repeat Treatment (VRT)	Participants in the VT who received VOLITE repeat treatment	As treated
Fitzpatrick Safety Cohort	Participants who were enrolled under protocol amendment 2 or above with Fitzpatrick skin phototype V or VI and meet any of the conditions including (1) baseline ACSS score of 1 in either cheek, (2) asymmetric baseline ACSS score of 2 or 3, or (3) FACE-Q overall converted score greater than 69	As treated

5. Statistical Analyses

5.1. General Considerations

- The primary analysis will be performed after the database is locked and randomization schedule is released.
- To account for different timing of VOLITE treatment and comparable time frame of data collection to enhance interpretability of effectiveness and safety analyses, the statistical analyses will be performed by the study periods defined below in [Table 5-1](#). For participants randomized to the treatment group, the Treated Period (TP) is the Control Period (CP) plus the Follow-up Period; for participants randomized to the control group, the TP is the Follow-up Period composed of the delayed treatment period plus the delayed treatment follow-up period ([Figure 1-1](#)). Follow-up Period starts on the end date of CP + 1 and ends on the same day as TP.

Table 5-1 Definition of the Control, Treatment, and Repeat Treatment Periods by Randomization Group

Randomization Group	Period	Treatment Group Label	Start Date	End Date
Treatment	Control Period (CP)	VOLITE	Initial treatment date	
The end date is the date of the Month 1 assessment:
 
 • If multiple assessments fall into Month 1 window, the date of the assessment included in the Month 1 analysis will be used as end date. • For participants who exit before Month 1, the end date is study exit date. • For participants with a missing assessment at Month 1, the end date is the target day for Month 1.
	Treated Period (TP)	VOLITE	Initial treatment date	Date of repeat treatment or the study exit date, whichever is earlier
	Repeat Treatment Period (RP)	VOLITE	Repeat treatment date	Study exit date
Control	CP	Control	Randomization date	
For participants who do not receive optional treatment:
 
 • If multiple assessments fall into Month 1 window, the date of the assessment included in the Month 1 analysis will be used as end date. • For participants who exit before Month 1, the end date is study exit date. • For participants with missing assessment at Month 1, the target day for Month 1 (Day 31) will be the end date. 
For participants who receive optional treatment: the end date is the date of optional treatment.

	TP	VOLITE Post-Control	Optional treatment date	Study exit date

- The start and end of treatment periods listed above for the mis-treated participants (ie., randomized to Treatment and did not receive Volite or randomized to Control and was treated with Volite prior to the primary timepoint) will be determined based on the treatment received.
- For CP, effectiveness analyses and baseline characteristics will be performed on the mITT population using the “as-randomized” assignment.

JUVÉDERM VOLITE™ XC

- For TP, effectiveness and safety summaries will be performed on the VT population by treatment group.
- For RP, effectiveness and safety summaries will be performed on the VRT population.
- The baseline for applicable effectiveness endpoints and safety parameters will be the last non-missing assessment on or before the latter of randomization date or first treatment date in the control period
- The change from baseline values will be computed as the post-baseline value minus the baseline value.
- Continuous variables will be summarized by number of participants with observed values (n), mean, standard deviation (SD), median, 1st and 3rd quartiles (Q1, Q3), minimum (min), and maximum (max). Categorical variables will be summarized by the number of participants with observed values or events (n), frequency count (N1), and percentage of participants with observed values or events.
- All statistical hypothesis tests will be performed at the 2-sided 5% significance level, unless stated otherwise.
- In general, statistical analyses will be performed using SAS version 9.4 or higher. Adverse events (AEs) and medical history will be coded using the Medical Dictionary for Regulatory Activities (MedDRA) version 22.1 or higher.
- WHO Drug Dictionary will be used to code medications.

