3.2 Background

JUVÉDERM VOLITE XC (HA concentration 12 mg/mL) is the newest member of the VYCROSS® technology platform, which includes JUVÉDERM VOLBELLA® XC (15 mg/mL, FDA-approved in 2016), JUVÉDERM VOLLURE™ XC (17.5 mg/mL, FDA-approved in 2017), and JUVÉDERM VOLYUMA® XC (20 mg/mL, FDA-approved in 2013). Each VYCROSS product is specifically tailored for its relative clinical use (lift capacity and spreadability), with JUVÉDERM VOLITE XC having the lowest HA concentration to serve the unmet need of a filler for fine lines. JUVÉDERM VOLITE XC also contains 0.3% lidocaine (w/w gel) to reduce injection pain and uncrosslinked HA to ease filler extrusion, which is the same amount of lidocaine and uncrosslinked HA included in VOLBELLA and VOLYURE.

The safety of JUVÉDERM VOLITE XC is supported by preclinical biocompatibility data, which show that it is nontoxic, noncytotoxic, nongenotoxic, nonirritant, nonsensitizing, noncarcinogenic, and nonpyrogenic.

A prospective, single-arm European postapproval study (V12-001) was conducted at a single center (6 injecting physicians from 6 countries) to assess the safety and effectiveness of JUVÉDERM VOLITE without lidocaine in treating fine lines and skin roughness in the face and neck. Treatment was administered on both sides of the face (cheek and forehead) and neck (if desired) for fine lines and the improvement in skin roughness. For 131 treated subjects, a total of 261 cheeks, 120 foreheads, and 96 necks were treated. Touch-up treatments were provided for 31 subjects (23.7%) and 46 cheeks (17.6%), and repeat treatments at 9 months were provided for 62 subjects (47.3%) and 124 cheeks (47.5%). The responder rate on the ACSS (formerly known as the Allergan Skin Roughness Scale) was 96.2% at Month 1, 76.3% at Month 4, 34.9% at Month 6, 15.8% at Month 9, and 87.1% at 1 month after repeat treatment. Among treated cheeks with scores of moderate or severe at baseline on the ACSS, the ACSS responder rate was 89.4% at Month 1, 66.7% at Month 4, 40.5% at Month 6, 15.6% at Month 9, and 94.3% at 1 month after repeat treatment. A statistically significant improvement ($p < 0.001$) in subject satisfaction with

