5.6.3. Adverse Events

An AE will be considered a treatment emergent adverse event (TEAE) if the AE began or worsened (increased in severity or became serious) after first administration of VOLITE for the treatment group and after the date of randomization for the control group. A TESAE is defined as an SAE that is also a TEAE. Overall summary will be provided on a per-participant level for TEAEs, treatment-related TEAEs, TESAEs, deaths, and TEAEs leading to study intervention discontinuation.

If more than one event is coded to the same PT for the same participant, the participant will be counted only once for that PT using the greatest severity for the summarizations by severity and most related occurrence for the summarizations by relationship to study intervention. If the severity of a TEAE is missing, the maximum severity will be assigned to the event for the summarization by severity. The value will be displayed as missing in the data listing. If the relationship to the study intervention is missing for a TEAE, the event will be considered related to the study intervention for the summarization. The value will be displayed as missing in the data listing.

TEAEs will be summarized by treatment group for CP using the Safety population. TEAEs will also be summarized for TP and RP using the VT and VRT populations, respectively.

The number and percentage of participants with TEAEs and the events in the following AE categories will be summarized for the above populations as described in [Table 5-8](#). For participants who received repeat treatment, their AEs reported during the first month in the initial treatment period will be summarized and presented in parallel with AEs reported during the repeat treatment period.

JUVÉDERM VOLITE™ XC

Summary tables will be provided for participants with TESAEs and participants with TEAEs leading to discontinuation if these occurred in 5 or more participants. Listings of all TEAEs, AESIs, TESAEs, TEAEs leading to discontinuation, and death will be presented.

Table 5-8 **TEAE Summaries**

Endpoint	Description	Timing	Methodology

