6.4. Data Handling Convention

6.4.1. Analysis Window

6.4.1.1. Effectiveness

Table 6-2, [Table 6-3](#), and [Table 6-4](#) below present the timepoints assigned for analyses and the corresponding range of study days for all the scheduled and unscheduled visits with complete dates. If a scheduled visit with incomplete date is available with no other visits with complete date during the visit window, then the visit with incomplete date may be used for analysis and the nominal visit will be used as the visit window (eg, if the only assessment collected for Month 2 visit window is on a Month 2 eCRF with incomplete date, then those data will be used for the Month 2 assessments).

If multiple assessments were taken within an analysis window, the assessment obtained on the day closest to the target day will be used; in the case of a tie, the assessment obtained on the later day will be used in the analysis.

Analysis visit windows for effectiveness endpoints are defined as follows:

If analysis date \geq reference date, then

$$\text{Analysis day} = \text{analysis date} - \text{reference date} + 1$$

If analysis date $<$ reference date, then

$$\text{Analysis day} = \text{analysis date} - \text{reference date}$$

Table 6-2 **Effectiveness Analysis Visit Definitions for Treatment Group and Control Group during Treated Period**

Scheduled Visit for Effectiveness Measure	Target Day of the Visit	Analysis Visit Window
Screening ^a	N/A	Screening visit; no more than 30 days prior to randomization
Baseline	N/A	Randomization/Initial Treatment visit
Last Treatment ^b	Day 1 of Last Treatment	Day 1
Month 1	Day 31 Post Last Treatment	Day 2 to Day 46
Month 2	Day 61 Post Last Treatment	Day 47 to Day 91
Month 4	Day 121 Post Last Treatment	Day 92 to Day 151
Month 6	Day 181 Post Last Treatment	Day 152 to Repeat Treatment Date (if applicable) or Study Exit Date, whichever is earlier

^a Participants may have screening and randomization on the same day. In such cases, only randomization visit is relevant

^b The last treatment refers to the latter of initial treatment or touch-up treatment (if applicable)

Table 6-3 Effectiveness Analysis Visit Definitions for Control Group during Control Period

Scheduled Visit	Target Day of the Visit	Analysis Visit Window
Randomization Day	Day 1	N/A
Month 1	Day 31	Day 2 to Optional Treatment Date or Study Exit Date, whichever is earlier.

Table 6-4 Effectiveness Analysis Visit Definitions for Treatment Group during Repeat Treatment Period

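### The Control Period is about a month longer for VOLITE participants who have a touch-up, so all-cause AE percentages in the only table with an untreated arm mix treatment effect with extra follow-up

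*SAP*

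**What the plan says.** SAP 5.1 introduces the Control, Treated and Repeat Treatment Periods as a way to handle the different timing of VOLITE treatment and to give a "comparable time frame of data collection to enhance interpretability of effectiveness and safety analyses, the statistical analyses will be performed by the study periods".

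Table 5-1 starts the VOLITE CP on the initial treatment date. On its close, the table says: "The end date is the date of the Month 1 assessment". SAP Section 2 fixes when that is: "Month 1 refers to 1 month after the preceding treatment (initial or touch-up) for participants in the JUVÉDERM VOLITE XC treatment group". For controls, the clock starts at randomization instead. Table 6-2 sets the VOLITE target at "Day 31 Post Last Treatment", and its footnote b defines last treatment as the later of the initial and touch-up treatments. Touch-up is optional and falls 30 days after initial treatment (SAP 1.2).

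The control CP runs from randomization to the Month 1 assessment (target Day 31). For controls who take the optional injection, it runs to the date of that injection.

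SAP 5.6.3 then states: "TEAEs will be summarized by treatment group for CP using the Safety population". Table 5-8 gives counts and percentages. No person-time rate, common cut-off or report of CP length is specified. The Treated and Repeat Treatment Period summaries cover VOLITE-treated participants only.

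**The concern.** In a comparison with an untreated arm, background AEs should occur equally on both sides and cancel. That requires both arms to be observed for similar lengths of time. Here a touched-up VOLITE participant contributes about twice the observation time of a control, and a percentage of participants with an event rises with time observed even if treatment does nothing. Touch-up is decided after randomization by the treating investigator and the participant (Protocol 7.2), so the extra follow-up cannot be known in advance.

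CP is the only place where a reader can set VOLITE AEs against those of untreated participants. Part of any all-cause excess there could be extra follow-up, and the planned output gives no means of telling how much.

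**Working it through.** **The plan's own safety figure.** The SAP states no CP length by arm. The nearest stated figure is 95% power with 147 treated participants and 2% incidence: 1 − 0.98^147 = 0.949. It reproduces, concerns treated participants only, and is not affected by this point.

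**Nominal CP length**, counting the first day as Day 1:
- VOLITE without touch-up: 31 days.
- VOLITE with touch-up: 31 + 30 = 61 days.
- Control without optional injection: 31 days.
- Control with optional injection: up to 31 + 7 = 38 days, using the +7 day window for initial treatment in Protocol Table 2-4.

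**Visit windows.** Protocol Tables 2-3 and 2-4 allow −2/+7 days at Month 1 and, in Table 2-4, at touch-up. The grid of Table 2-2 (treatment group) could not be read, so the same windows are assumed. Elapsed CP is then 56–74 days with touch-up and 28–37 days without. For controls it is 28–37 days, or up to about 44 with the optional injection.

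**Mean VOLITE CP** = 31 + 30t, where t is the touch-up share.
- t = 23.7% (31 of 131 in study V12-001, Protocol 3.2): 31 + 7.1 = 38.1 days.
- t = 50% (assumed; no source in the documents): 46.0 days.

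**Mean control CP.** SAP Section 3 assumes 28 treated controls. That is 40% of the 70 randomized (one third of 210) or 50% of the 56 in the power calculation. Giving each the full 7 days is an upper bound.
- No extension: 31 days.
- 40% extended: 31 + 0.4 × 7 = 33.8 days.
- 50% extended: 31 + 0.5 × 7 = 34.5 days.

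**Ratio of mean CP, VOLITE to control:**

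| Touch-up share | Control 31 d | Control 33.8 d | Control 34.5 d |
|---|---|---|---|
| 23.7% | 1.23 | 1.13 | 1.10 |
| 50% | 1.48 | 1.36 | 1.33 |

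**Effect on a percentage.** Assume the same constant background AE rate in both arms and a 31-day risk of 10%.
- 61-day risk: 1 − 0.90^(61/31) = 18.7%.
- VOLITE at 23.7% touch-up: 0.763 × 10% + 0.237 × 18.7% = 12.1%.
- VOLITE at 50% touch-up: 14.4%.
- 38-day control risk: 1 − 0.90^(38/31) = 12.1%.
- Control: 10.0% with no extension; 0.6 × 10% + 0.4 × 12.1% = 10.8% with 40% extended; 11.1% with 50% extended.

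With no treatment effect at all, the CP table would be expected to show 12.1% against 10.0–11.1% at 23.7% touch-up, and 14.4% against 10.0–11.1% at 50%. With controls held at 31 days and a control risk anywhere from 5% to 30%, the spurious risk ratio is 1.16–1.22 at 23.7% touch-up and 1.34–1.46 at 50%.

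**The case against.** **Only a subset is affected.** A reader might infer that the whole VOLITE arm is followed for two months. It is not. Without touch-up, the Day 30 visit becomes Month 1 (Protocol Table 2-2, note b). This stands, and it is why the size depends on the touch-up rate.

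**The control arm is extended too.** Counting controls to the optional injection offsets part of the gap. If every control gained 7 days (38 days), the ratio would be 1.00 at 23.7% touch-up and 1.21 at 50%. This stands as an offset, but the SAP expects only 28 treated controls, so a gap of 10–13% remains at 23.7%. The rule also makes control follow-up depend on a choice made after randomization.

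**The touch-up rate may be lower.** V12-001 also treated forehead and neck. Its 46 touched-up cheeks imply between 23 and 31 participants with a cheek touch-up, or 17.6–23.7% of 131. At 17.6% mean VOLITE CP is 31 + 30 × 0.176 = 36.3 days, which is 5–17% longer than control. But that study had other volume limits, and this trial's rate could fall on either side.

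**The table is descriptive.** There is no AE test, and the artefact overstates VOLITE AEs. With 140 versus 70 participants, 2.1 points (12.1% against 10.0%) is under half the standard error of the difference: √(0.121 × 0.879/140 + 0.10 × 0.90/70) = 4.5 points. Treatment-related TEAEs are tabulated separately, and injection site responses by treatment. All of this stands, and it limits the point to all-cause summaries.

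**The quoted purpose covers all three periods.** It may chiefly mean aligning immediate and delayed VOLITE treatment. A reader might infer that the SAP promises equal CP length in both arms; it does not say so. It does, however, name safety analyses among those meant to gain from comparability.

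**AEs after touch-up belong to the regimen.** A reader might infer that the CP table should be replaced by one cut at touch-up. That would remove second-injection AEs from the only table with an untreated arm, so the planned table should stay.

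**Conclusion.** The point holds for all-cause TEAEs, TESAEs and discontinuations in CP. Their percentages mix treatment effect with extra follow-up in touched-up VOLITE participants. Mean VOLITE CP is about 23% longer at the prior study's 23.7% touch-up rate if controls are counted to Day 31, and about 10–13% longer if the 28 controls expected to be treated each gain the full 7 days. At an assumed 50% touch-up it is about 33–48% longer. These figures rest on nominal visit timing and a touch-up rate that the documents do not give for this trial. The AE percentages also rest on an assumed, constant background rate.

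A reader might go further and conclude that the CP excess says nothing about treatment. The documents do not support that: the artefact is modest at the only documented touch-up rate, and treatment-related TEAEs and injection site responses are little affected. The effectiveness definition of CP is not in question here. This is a cheap improvement to the reporting, not a flaw that undermines the safety assessment.

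**What to change.** Keep the planned CP TEAE table. In SAP 5.6.3 and Table 5-8, add beside it:

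1. TEAEs per 100 participant-months of CP, by arm.
2. A common-window summary of TEAEs with onset from Day 1 (initial treatment or randomization) to Day 31, cut at touch-up or at the optional injection.
3. CP duration by arm, and by touch-up status within the VOLITE arm.

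Items 1 and 2 complement each other: a rate assumes events are spread evenly over time, and the common window does not. With equal background rates, either brings the nominal ratio back to 1.00. SAP 5.6.3 already uses a first-month AE window for participants who receive repeat treatment, so the idea is not new to this plan.

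The cost is SAP wording, one date cut and a little more tabulation, with no new data. The common-window summary leaves out AEs after touch-up, but these stay in the planned CP and Treated Period tables.
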